## **8.0 Criteria for Response**

The principal investigator or his delegates will make the initial or preliminary determination of response at 14  $\pm$  1 days after end of therapy. Patients will be considered as a success if there are no signs (clinical and/or radiologic) or symptoms of progression to pneumonia at the end of study, that is 14  $\pm$  1 days after discontinuation of therapy or at week 4 of follow-up for patients on the observational arm. At the end of each winter season and without knowledge of the determination of response of the PI or delegates, an independent internal panel (1 expert in HSCT and 1 in Infectious Diseases to be determined) will review each case and determine failure (pneumonia) or success (no evidence of pneumonia) rate on each arm of the study. The panel will have the final determination of response.

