## 5.0 Treatment Plan

This is an open label randomised trial. All eligible patients will be randomized to receive ribavirin therapy either at the modified schedule of 60 mg/ml of the drug for a 3-hour period 3 times/day for at least 5 days by aerosolization via a SPAG-2 generator via a face mask **OR** patients will receive a one time loading dose of 10 mg/kg oral dose then 20 mg/kg orally (rounded to the nearest 200 mg dose) divided into three doses per day at a maximum of total dose of 1800 mg/day (therapeutic arms). The duration of either regimen is recommended to be up to 10 days but could be extended for more than 10 days at the discretion of the treating physician.

In addition, patients will receive inhalational bronchodilator therapy consistent of Xopenex 0.63 mg HHN every 6-8 hours as needed and as per standard of care. Patients may receive albuterol (2.5 mg per 3ml for adults) nebulization, if Xopenex is not tolerated. Patients will not be given IVIG or palivizumab for treatment of the RSV URI. Patients who develop evidence of LRI at any time will be considered reaching the primary endpoint and will be managed at the discretion of the treating physician as per standard of care (for example, patients can be treated by the standard or the modified aerosolized regimen with or without IVIG or palivizumab).

Patients with mild immunodeficiency who are at low risk (scoring of 0-2 on ISS) for progression and when treatment is not indicated for RSV URI as per standard of care (observational arm) will be followed prospectively once a week up to 4 weeks from the diagnosis of RSV.

For schedule of events tables see PDOL appendix I.

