## **7.0 Evaluation During Study**

7.1 Nasal washes for the therapeutic arm will be repeated on day 3  $\pm$  1 day, day 7 ( $\pm$  1 days), day 14 ( $\pm$  1 days), and by day 14  $\pm$  1 days after end of therapy; and will be stored at 6-8 degrees Celsius until it can be taken to [name] laboratory for analysis. Blood specimens for the therapeutic arm will be drawn at enrollment and 14  $\pm$  1 days after end of therapy. These specimens will be shipped for batch analysis to [name] laboratory at Baylor College of Medicine ([name]) for viral loads, titers and for neutralizing antibodies testing (Please see references 7-9 for methods). For patients on the observational arm, nasal washes for RSV viral loads will be done once a week for 4 weeks and blood specimens will be taken at enrollment and the 4th week on study for neutralizing antibodies testing and for RSV viral load. Leftover of blood and nasal washes will be saved at [name] laboratory for future testing.

7.2 Routine blood tests as in 6.3 will be repeated at least once weekly until study is completed as part of the standard of care for patients who are on the therapeutic arms. Patients on observational arm will have routine blood tests done at enrollment and the 4th week on study.

7.3 Patients will be monitored for signs and symptoms of URI and LRI (Please see Appendix G and H for Clinical Assessment Tool). Patients who are hospitalized will be seen 2 times a week from the time of enrollment until discontinuation of ribavirin therapy. Patients who are not hospitalized will be monitored twice a week until the discontinuation of therapy or once a week for 4 weeks for patients on the observational arm. Any possible evidence of pulmonary infection should be confirmed by a repeat chest radiographic study and/or oxygen saturation level. All patients on the therapeutic arms will have a final visit 14 days  $\pm$  1 days after end of therapy.

7.4 Follow-up after end of therapy or discontinuation of therapy: Patients will be seen 14 days  $\pm$  1 days after discontinuation of therapy for the final determination of response, unless there is progression to pneumonia. In the latter scenario or if study drug is discontinued for Serious Adverse Events (SAEs), patients will be followed for up to 14 days from the time of occurrence of the event or until resolution of the SAE whichever occurs last or up to 30 days from the last dose of the study drug.

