7.5 Physical Exams for the therapeutic arm will be done at day 3  $\pm$  1 day, day 7 ( $\pm$  1 days), day 14 ( $\pm$  1 days), and then 14 days ( $\pm$  1 days) after end of therapy. Concomitant medications that are used to treat LRI will be recorded day (3  $\pm$  1 day), day 7 ( $\pm$  1 days), and then at 14 days ( $\pm$  1 days) after end of therapy. Physical exams for observational arm will be done once a week for 4 weeks.

7.6 As standard of care, patients will have pulmonary function tests scheduled between 6-10 weeks after completing therapy for RSV.

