## 10.0 Cost Analysis

All patients who receive aerosolized ribavirin have to be hospitalized for the entire duration of the therapy, or even more depending on the patient condition. Patients who will be treated with oral ribavirin may be hospitalized at the discretion of the primary service. An average per day cost of keeping patients in hospital for ribavirin administration will be obtained from the financial department and institutional records and will be used to calculate the total cost of treating patients with ribavirin using the following formula:

Total cost of treating the patients with ribavirin (aerosolized or oral) = cost of keeping the patient in-hospital per day for RSV  $\times$  total number of days the patient is kept in hospital + cost of the drug (aerosolized and oral ribavirin) and its administration (for aerosolized ribavirin).

This will be compared to the total cost of administering oral ribavirin on an outpatient basis by adding the total cost of the drug and the follow up visits. In either arm of the study, if a patient progresses to pneumonia, the total cost of treating the patient with aerosolized ribavirin (if applicable) will be calculated using the above formula and added to the total cost.

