## **12.0 Reporting Requirements & Drug Accountability**

A case report form will be required for each patient entered on study (please see appendix G and H). An interim safety analysis of the data focusing on SAEs will be done after each winter season.

We will maintain the study drug records of aerosolized ribavirin including documentation of the amount received and duration as per respiratory therapy protocol. For oral ribavirin, subjects should bring their medication bottles back at each visit even if they are empty so site personnel can assess study drug compliance.

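### Section 8.0 does not say that the panel deciding pneumonia is masked to treatment arm, so this open-label primary endpoint is open to assessment bias in either direction

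*Combined protocol and SAP*

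**What the plan says.** Section 5.0 is explicit on treatment masking: "This is an open label randomised trial". Section 2.0 says double blinding is not feasible because too few patients are available each year. It does not discuss masking the outcome assessment.

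Under section 8.0 the investigator or delegates make a preliminary call 14 days after therapy ends. At the end of each winter season, and "without knowledge of the determination of response of the PI or delegates, an independent internal panel" (one HSCT expert and one infectious diseases expert) "will review each case and determine failure (pneumonia) or success (no evidence of pneumonia) rate on each arm of the study". The section closes: "The panel will have the final determination of response". Section 11.0 makes pneumonia by day 14 after therapy the primary outcome, so the panel's call is the primary endpoint.

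Some confirmation is required. Section 7.3 says: "Any possible evidence of pulmonary infection should be confirmed by a repeat chest radiographic study and/or oxygen saturation level". Section 9.1 defines failure as pulmonary infection due to RSV, documented by chest imaging and/or low oxygen level.

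**The concern.** The authors considered what to withhold from the panel and listed one item, the investigator's determination. Treatment arm is not listed, and no other supplied section masks the panel to it. Asking the panel for a rate by arm, read literally, requires arm labels, although the phrase may only describe how results are reported.

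Unredacted files would normally give the arm away:

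- Section 10.0: "All patients who receive aerosolized ribavirin have to be hospitalized for the entire duration of the therapy", whereas oral patients may be outpatients.
- Section 12.0: respiratory-therapy records exist for the aerosol arm, and "For oral ribavirin, subjects should bring their medication bottles back at each visit even if they are empty".
- Section 9.1: an oral patient who develops LRI may be switched to aerosol.

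Separately, section 7.5 says "Concomitant medications that are used to treat LRI will be recorded". Those entries hint at the treating team's opinion and so weaken the one masking safeguard the plan does state.

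The oxygen threshold is objective. Reading an infiltrate, weighing symptoms and attributing pneumonia to RSV are not. If the panel can see the arm, a lenient reading of oral cases favours a non-inferiority claim, and a stricter reading of oral cases costs power. The text rules out neither.

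**Working it through.** **Inputs from section 11.0.** Expected failure rates: aerosol 0.20, oral 0.15. Margin 0.10, 38 patients per arm, one-sided level 0.20, power 0.80. One futility look at 38 of 76 patients (half the information), with nominal levels 0.6040 at the look and 0.2116 at the end.

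**Model.** Normal approximation with unpooled variance, ignoring the risk strata:

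- SE = √[p_o(1−p_o)/38 + p_a(1−p_a)/38]
- Expected final Z: θ = [0.10 − (p_o − p_a)]/SE. The interim mean is θ√0.5, and corr(Z1, Z2) = √0.5.
- Continue if Z1 > −0.264 (level 0.6040). Claim non-inferiority if Z2 > 0.801 (level 0.2116).

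**Reproducing the design.**

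- At the margin (oral 0.30, aerosol 0.20): θ = 0, and the probability of a claim is 0.200.
- At the design rates (oral 0.15, aerosol 0.20): SE = 0.0870, θ = 0.15/0.0870 = 1.72, and power is 0.803.

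Both match the plan.

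**One patient.** 1/38 = 2.6 percentage points.

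**Assumed error rates.** The documents give none, so these are illustrations. The oral-only columns put all the error in the oral arm, which is the harmful direction. The last column applies the same error rate to both arms, as a masked panel roughly would.

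*Under-calling a fraction q of true pneumonias, true rates at the margin; observed oral rate = 0.30(1−q):*

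| q | Oral patients affected | Observed oral rate | False claim, oral only | False claim, both arms |
|---|---|---|---|---|
| 0 | 0 | 0.30 | 0.200 | 0.200 |
| 0.10 | 0.10 × 11.4 = 1.1 | 0.27 | 0.296 | 0.230 |
| 0.20 | 0.20 × 11.4 = 2.3 | 0.24 | 0.414 | 0.266 |

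(11.4 = 0.30 × 38.)

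*Over-calling a fraction s of non-cases, true rates as designed; observed oral rate = 0.15 + 0.85s:*

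| s | Oral patients affected | Observed oral rate | Power, oral only | Power, both arms |
|---|---|---|---|---|
| 0 | 0 | 0.150 | 0.803 | 0.803 |
| 0.025 | 0.025 × 32.3 = 0.8 | 0.171 | 0.718 | 0.778 |
| 0.05 | 0.05 × 32.3 = 1.6 | 0.193 | 0.626 | 0.757 |
| 0.10 | 0.10 × 32.3 = 3.2 | 0.235 | 0.435 | 0.719 |

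(32.3 = 0.85 × 38.)

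**Check without the normal approximation.** A binomial simulation of the oral-only cases (1,000,000 runs, Wald Z) gave 0.197, 0.296 and 0.419 for q = 0, 0.10 and 0.20, and 0.815, 0.732 and 0.640 for s = 0, 0.025 and 0.05. The pattern is the same.

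**The case against.** The strongest reply has four parts.

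1. **The plan is silent, not wrong.** Reporting a rate by arm need not mean that the panel sees arm labels, and Appendices G and H (assessment tools and case report form) were not available to check. This stands as a limit on confidence. It does not fill the gap: section 8.0 sets out the panel's procedure and refers to no appendix.

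2. **There are real safeguards.** The panel is described as independent, does not see the investigator's determination, and rules on cases supported by imaging or oximetry. These narrow the room for error. Independence from the investigator's call is still not masking to arm, and imaging still has to be interpreted and attributed.

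3. **The oral-only figures overstate what masking gains.** A masked panel would also make errors, spread over both arms. This is correct. Against the equal-error column, the gain is about 7 or 15 points of false non-inferiority (0.296 − 0.230; 0.414 − 0.266) and about 6, 13 or 28 points of power (0.718 against 0.778; 0.626 against 0.757; 0.435 against 0.719). The 10% over-calling case, about 3 of 32 oral non-cases and none on aerosol, is a stress test.

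4. **Masking will be partial.** Hospitalization hints at arm, and unmasked staff still decide when to obtain confirmatory imaging. Both points stand. They limit the benefit but are no reason to leave the panel unmasked.

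That this is a phase II screening trial argues against treating the point as critical. Equally, a one-sided level of 0.20 leaves little room for added error.

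**Conclusion.** The concern holds. As written, section 8.0 allows a panel that can see the treatment arm to decide a partly judgemental non-inferiority endpoint. Infeasibility of double-blind treatment is no obstacle to masked review of existing records.

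A net shift of one to three calls in one arm is enough to change the trial's error rates materially. The size of any actual bias is unknown: the error rates above are assumed, the oral-only results are worst-direction illustrations, and the equal-error comparison is the fairer guide to what masking could recover. This is a change the sponsor should make. Confidence is medium, because the text is silent on arm rather than explicit that the panel sees it, and two appendices could not be checked.

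**What to change.** In section 8.0:

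- State that the panel is masked to treatment arm as well as to the investigator's determination.
- Give the panel packets with arm, route, aerosol-generator and respiratory-therapy records, ribavirin orders, drug-return records and LRI treatment changes removed, and with admission details removed as far as the clinical picture allows.
- Change the panel's task from a rate by arm to an outcome for each patient.
- Lock the panel's calls before the statistician attaches arm and computes rates. Do this for the futility analysis as well as the final one.

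The cost is a short addition to section 8.0 and coordinator time to redact about 38 packets per season (76 randomized patients over 2 seasons). Redacting serial clinical records is real work, but the panel and the sample size stay the same and patient care is untouched. The up to 20 observational patients do not enter the randomized comparison, so their files need not be redacted for this purpose. If the panel was always meant to be masked to arm, stating it and describing the packets settles the point.

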### *Sample Size*

We expect that 20% of patients randomized to aerosolized ribavirin will be considered treatment failures, and we expect that 15% of patients randomized to oral ribavirin will be considered treatment failures. With a non-inferiority margin of 10%, a sample size of 38 patients per

treatment arm will yield 80% power to reject the following null hypothesis with a 1-sided significance level of 0.20:

$$H_0: \pi_{\text{oral}} - \pi_{\text{aerosol}} \geq 0.10$$

$$H_1: \pi_{\text{oral}} - \pi_{\text{aerosol}} < 0.10$$

where  $\pi_{\text{aerosol}}$  is the treatment failure rate for aerosolized ribavirin and  $\pi_{\text{oral}}$  is the treatment failure rate for oral ribavirin. We expect to enroll these patients over 2 winter seasons.

This sample size calculation includes an interim analysis for futility using the methods of Lan and DeMets (1983) with an O'Brien-Fleming (1979) stopping boundary. The futility analysis will be conducted once 38 patients have been evaluated for treatment failure. We expect the timing of this futility analysis to be after the first winter season of the study. The nominal significance level for this futility analysis is 0.6040, and the nominal significance level at the end of the study is 0.2116.

This sample size calculation was performed using East 5.2 (Copyright © 2008, Cytel Inc., Cambridge, MA).

For the observational arm, up to 20 patients will be enrolled for a total of 96 patients for the whole trial.

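### Section 8 has the endpoint panel determine failure rates by arm each season, so it can know the season-1 comparison when it adjudicates later cases

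*Combined protocol and SAP*

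**What the plan says.** Section 8.0 (Criteria for Response) sets the timing of the review: "At the end of each winter season and without knowledge of the determination of response of the PI or delegates, an independent internal panel" of one transplant expert and one infectious-disease expert, not yet named. Its task is stated in one clause: it is to go through every case and "determine failure (pneumonia) or success (no evidence of pneumonia) rate on each arm of the study". Its authority is stated in the next sentence: "The panel will have the final determination of response".

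Section 5.0 says of the design: "This is an open label randomised trial". The panel is kept from the investigator's own determination. Nothing says that it is masked to treatment arm.

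Section 11.0 (Sample Size) plans one interim analysis, for futility only: "The futility analysis will be conducted once 38 patients have been evaluated for treatment failure", expected after the first season. On accrual it says: "We expect to enroll these patients over 2 winter seasons". Section 11.0 does not mention the panel, and no section says who may see outcome rates by arm while the trial is running.

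**The concern.** An adjudication panel needs to decide one thing per patient: pneumonia or not. Section 8.0 gives it a second product, the comparative primary result, and does so part-way through. After season 1 the panel would know which arm is ahead, and would then give the final call on the patients still to come.

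Those calls involve judgement. Under Section 8.0, success depends on the absence of clinical and/or radiologic signs and of symptoms. Under Section 9.1, failure requires lung infection attributed to RSV, shown by imaging and/or oxygen level. A borderline infiltrate in season 2 could, without intent, be read in the light of the season-1 rates. With 38 patients per arm, one changed call moves an arm's failure rate by 1/38 = 2.6 percentage points, against a 10-point margin.

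**Working it through.** **1. Is this an extra look?** Setting the schedules side by side:

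| Event | Trigger | Expected time |
|---|---|---|
| Panel review 1 | End of season 1 | End of season 1 |
| Futility analysis | 38 patients evaluated | After season 1 |
| Panel review 2 | End of season 2 | End of accrual |
| Final analysis | 76 patients evaluated | End of study |

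If accrual goes to plan, review 1 falls at the futility analysis and is its natural source of data, and review 2 feeds the final analysis. A separate mid-trial compilation arises only if accrual runs beyond two seasons, or if the 38th evaluated patient does not fall at a season's end.

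**2. Does it change the design's error rates?** The inputs, all from Section 11.0, are failure rates of 20% (aerosol) and 15% (oral), margin 0.10, one-sided level 0.20, power 80%, 38 per arm, and one futility look at information fraction 38/76 = 0.5.

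- Variance term: 0.20×0.80 + 0.15×0.85 = 0.2875. Distance from the margin: 0.10 − (0.15 − 0.20) = 0.15.
- Fixed design: n = 0.2875 × (2 × 0.8416)² / 0.15² = 36.2, so 37 per arm.
- O'Brien-Fleming-type spending of beta = 0.20 at half information: 2 − 2Φ(1.2816/√0.5) = 0.0699.
- Solving the two-stage design with a binding futility bound gives 37.6, so 38 per arm, and nominal levels 0.6040 and 0.2116. All three match the plan.
- With the stated bounds (Z = −0.264 at the interim, 0.801 at the end; correlation √0.5), type I error = P(Z₁ ≥ −0.264 and Z₂ ≥ 0.801) = 0.2000. With drift 0.15/√(0.2875/38) = 1.725, power is 0.803.

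Section 8.0 attaches no test, boundary or decision to the panel's rates, so 0.2000 is unchanged.

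**3. How large could the operational bias be?** The documents give no rate of changed calls, so this is illustration only. I enumerated the trial exactly with 19 and then 38 per arm, an unpooled z test (a simplification of the planned stratified test), and true failure rates at the null boundary (30% oral, 20% aerosol). With no bias, type I error is 0.197. Let b be the assumed proportional shift in second-half failures, driven by who led at the interim:

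| Assumed behaviour in season 2 | b = 5% | b = 10% | b = 20% |
|---|---|---|---|
| Oral failures cut by b if oral leads, raised by b if it trails | 0.198 | 0.199 | 0.202 |
| Failures cut by b in whichever arm leads | 0.200 | 0.203 | 0.209 |
| Oral failures cut by b only when oral leads | 0.205 | 0.212 | 0.226 |

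The effect is small because, at the null boundary, oral leads at the interim in only 18% of trials.

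**The case against.** The strongest reply is that the sentence is merely awkward. It may mean that the panel classifies cases and that rates follow from those calls. Section 11.0 describes the tabulation and testing and gives the panel no part in them. That reading is possible, but the words assign the rate on each arm to the panel, and a site following them literally would produce the comparison.

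A second reply is that, in an open-label trial, the investigators already make a preliminary determination for each patient, so staff can see outcomes by arm without the panel. That stands, and it limits what the fix achieves. It does not justify giving the comparison to those who have the final say on the endpoint.

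Stronger readings are tempting, and the documents do not support them:

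- **An unplanned efficacy look that inflates alpha.** Declaring non-inferiority on the season-1 rates would raise type I error to 0.282 (tested at 0.20) or 0.289 (at 0.2116). The plan provides for no such early claim.
- **A type I error of 0.218, 0.240 or 0.286.** These follow if 5%, 10% or 20% of true second-half oral pneumonias are overturned in every continuing trial. That is a fixed bias in favour of oral therapy. It needs no knowledge of season-1 rates, so it does not measure this problem.
- **The same two individuals throughout.** One panel is described and no rotation is mentioned, so continuity is the natural reading. Fixed membership is nevertheless an inference.

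**Conclusion.** The point holds as one of operational bias and confidentiality. Read literally, Section 8.0 gives the final adjudicators the primary result by arm with about half the randomised patients still to be judged, and no section limits who else sees it. It does not add a formal analysis on the expected schedule, and it leaves the nominal type I error at 0.2000.

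The documents cannot supply the size of the bias. The trend-following illustration suggests a modest effect on type I error (0.198 to 0.209, at most 0.226, against 0.197), and it rests entirely on assumed overturn rates and an unstratified test. The conclusion also assumes that the panel carries on from season 1 to season 2, or that its rates pass to whoever does. The change is worth making because it removes an avoidable source of bias at almost no cost, not because a large error has been shown.

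**What to change.** Reword Section 8.0 so that the panel returns only a determination for each case (pneumonia or no pneumonia) and neither compiles nor receives results by arm. Add that the trial statistician alone tabulates outcomes by arm, once for the planned futility analysis and once at the end, and that only a stop or continue decision is released in between.

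The cost is one or two sentences, with no extra patients, staff or procedures. The downside is that rates by arm are not available to the panel or investigators between seasons. The rewording does not by itself stop a panel from keeping its own tally if the case files show the treatment arm. The plan is silent on that, and it should be settled in the same edit.
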